6.2 REFERENCE START DATE AND STUDY DAY

Reference start date is defined as the date of the first dose of study Fabrazyme after enrolment.

Study Day will be calculated from the reference start date and will be used to show start/stop day of assessments and events. It will appear in every listing where an assessment date or event date appears.

• If the date of the event is on or after the reference date, then: Study Day = (date of event –

Document: \\ieedo

vnasc01\BIOSdata\Sanofi\Fabrazyme\IAB16602\Biostatistics\Documentation\SAP\SAP\Sanofi\Final

Version\lps17726-16-1-9-sap.docx

Author: Version Number: Final V1.0

Version Date: 22Oct2024

Template No.: CS_TP_BS016 Revision 7 Reference: CS_WI_BS005

Effective Date: 01Nov2021

PROTOCOL LPS17726

Analysis Plan Template

Page 26 of 65

reference start date) + 1 (Day 1 is the day of the first dose of study Fabrazyme after enrolment).

• If the date of the event is prior to the reference date, then: Study Day = (date of event – reference start date).

In the situation where the assessment or event date is partial, the date will appear partial in the listings. If the assessment or event date is missing the date will also appear missing in the listings. Study Day and any corresponding durations will not be derived for any missing or partial assessment/event dates and will therefore appear missing in the listings.

6.3 BASELINE

Unless otherwise specified, baseline is defined as the last observed value, including unscheduled visits, prior to the first date and time of study Fabrazyme infusion after enrolment.

If the last non-missing measurement and reference start date and time coincide that measurement will be considered baseline if the assessment is planned per protocol to take place prior to first administration of study medication during the study treatment period.

6.4 DERIVED TIMEPOINTS

For the below definitions a treatment completer is defined as a participant who has either reached the target infusion duration of their cohort or completed the study treatment period and experienced at most 1 IAR. A study completer is defined as a participant who has enrolled into the study through providing informed consent, been allocated to the study treatment, completed the study treatment period, and attended their last follow-up visit.

End of Treatment (EOT) visit is derived for participants who are administered at least one infusion during the study treatment period and is defined as the last recorded visit for which the participant receives study Fabrazyme. For treatment completers this occurs when the participant

Document: \\ieedc

vnasc01\BIOSdata\Sanofi\Fabrazyme\IAB16602\Biostatistics\Documentation\SAP\SAP\Sanofi\Final

Version\lps17726-16-1-9-sap.docx

Author: Version Number: Final V1.0

Version Date: 22Oct2024

Reference: CS_WI_BS005

Template No.: CS_TP_BS016 Revision 7

Effective Date: 01Nov2021

PROTOCOL LPS17726

Analysis Plan Template

Page 27 of 65

either successfully reaches the target infusion duration for the cohort or reaches the end of the study treatment period and does not experience two IARs. For non-treatment completers their EOT visit is defined as the last recorded visit prior to or on treatment discontinuation for any reason.

End of Study (EOS) visit for a participant is defined as their last recorded visit in the study. For study completers their EOS visit will be their last follow-up visit recorded 28 weeks after their first Fabrazyme administration. For non-study completers their EOS visit is defined as their last recorded visit prior to or on study withdrawal. For screen failures their EOS will be recorded as 'Screening'.

6.5 RETESTS, UNSCHEDULED VISITS AND EARLY TERMINATION DATA

For by-visit summaries, data will be assigned to visits based on the windowing rules provided in SAP Section 6.6 'Windowing Conventions'. Measurements taken at unscheduled visits (including retests) can be considered for the by-visit summaries (as per the visit windowing rules).

6.6 WINDOWING CONVENTIONS

A windowing convention will be used to determine the analysis visit value for a given measurement. Exploratory Laboratory Parameters and Vital Signs are subject to the following windowing conventions.

All scheduled study visits are defined relative to the reference start date.

Assessments with a partially known or missing assessment date will not be considered for analysis windowing.

Observations that fall outside of a visit window will be identified as "Out of Window" and will be listed only and not used in any by visit summary tables or analyses where visit is used.

Document: \\ieedc

 $vnasc01\\BIOS data\\Sanofi\\Fabrazyme\\IAB16602\\Biostatistics\\Documentation\\SAP\\SAP\\Sanofi\\Finally and the properties of t$

Version\lps17726-16-1-9-sap.docx

Author: Version Number: Final V1.0

Version Date: 22Oct2024

Template No.: CS_TP_BS016 Revision 7 Reference: CS_WI_BS005

Effective Date: 01Nov2021

Page 28 of 65

6.6.1 EXPLORATORY ENDPOINTS

The windowing convention for the exploratory laboratory measurements are wider to those in the protocol and are provided in the below table.

Table C - Analysis Window for Exploratory Endpoints

Assigned	Study Day	Visit	Week Assigned	Target Day
(Inclusive)		Assigned		
From	То			
1	6	Visit 2	Week 0	1
7	21	Visit 3	Week 2	14
22	34	Visit 4	Week 4	28
35	48	Visit 5	Week 6	42
49	62	Visit 6	Week 8	56
63	76	Visit 7	Week 10	70
77	90	Visit 8	Week 12	84
91	104	Visit 9	Week 14	98
105	153	Visit 10	Week 16	112
154	210	Visit 11	Week 28	196

If one or more result for a variable falls within the same visit window, the result with the date closest to (but before) the start date of infusion of the study drug will be used for post-baseline by visit summaries.

6.6.2 VITAL SIGNS

The windowing convention for vital signs are the same as for exploratory endpoints and are provided in the below table.

Document: \\ieedc-

 $vnasc 01\BIOS data \Sanofi\Fabrazyme \IAB16602\Biostatistics \Documentation \SAP\Sanofi\Final \BIOS data \Sanofi\Fabrazyme \BIOS data \Sanofi\Fabrazyme \BIOS data \BIOS data \Sanofi\Fabrazyme \BIOS data \BIO$

[figure not shown]
Version\lps17726-16-1-9-sap.docx

Author: Version Number: Final V1.0

Version Date: 22Oct2024

Template No.: CS_TP_BS016 Revision 7 Reference: CS_WI_BS005

Effective Date: 01Nov2021

Page 29 of 65

Table D: Analysis Windows for Vital Signs

Assigned Study Day (Inclusive)		Visit Assigned	Week Assigned	Target
				Day
From	То			
-28	-1	Screening	Screening	-1
1	6	Visit 2	Week 0	1
7	21	Visit 3	Week 2	14
22	34	Visit 4	Week 4	28
35	48	Visit 5	Week 6	42
49	62	Visit 6	Week 8	56
63	76	Visit 7	Week 10	70
77	90	Visit 8	Week 12	84
91	104	Visit 9	Week 14	98
105	153	Visit 10	Week 16	112
154	210	Visit 11	Week 28	196

If one or more result for a variable falls within the same visit window, the following rules will be applied to select the appropriate value to be used for post-baseline by visit summaries.

Only the vital signs assessed prior or after an infusion of the study drug, on the day of the infusion, are considered. The following rules apply (note that pre-infusion and post-infusion assessments should be considered separately):

- Take the result with the date closest to the target day.
- If two assessment dates are equidistant from the Target Day, take the earlier assessment.
- If more than one assessment is on the same date, take the latest based on time.
- If time is not available and it cannot be determined whether the assessment was prior to or after the infusion, then the result will be considered missing.

Document: \\ieedc

 $vnasc 01\BIOS data \Sanofi\Fabrazyme \IAB16602\Biostatistics \Documentation \SAP\SAP\Sanofi\Final \BIOS data \Sanofi\Fabrazyme \BIOS data \BIOS data \Sanofi\Fabrazyme \BIOS data \$

Version\lps17726-16-1-9-sap.docx

Author: Version Number:

Version Date: 22Oct2024

Final V1.0

Template No.: CS_TP_BS016 Revision 7 Reference: CS_WI_BS005

Effective Date: 01Nov2021

PROTOCOL LPS17726

Analysis Plan Template

Page 30 of 65

Final V1.0

22Oct2024

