8.4 Safety Assessments

8.4.1 Vital Signs

Body temperature, heart rate, respiratory rate, and blood pressure will be assessed before and 1 hour after the completion of each infusion.

Blood pressure and heart rate measurements will be assessed with a completely automated device. Manual techniques will be used only if an automated device is not available.

Blood pressure and heart rate measurements should be preceded by at least 5 minutes of rest for the participant in a quiet setting without distractions (eg, television, cell phones).

Three readings of blood pressure and heart rate will be taken. The first and second readings should be rejected. The third reading should be recorded.

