16.4.5 ANALYSIS OF VITAL SIGNS AND WEIGHT

Vital signs data will be analyzed for the SAF analysis set for the following parameters:

- Systolic blood pressure (mmHg)
- Diastolic blood pressure (mmHg)
- Heart rate (bpm)
- Respiratory rate (bpm)
- Body temperature (°C)
- Weight (kg)

The following summaries based on observed data will be provided for the study treatment period:

- Values at each visit.
- Change from baseline at each visit for pre-dose vital signs.
- Change from pre-dose to post-dose at each visit (for all parameters except weight [kg])
- Incidence of predefined markedly abnormal criteria by age group and parameter.

Participants who have markedly abnormal values in both directions (abnormally high and abnormally low) during the study treatment period for the same parameter will be included in both high and low counts for that parameter.

Corresponding listings will also be provided detailing the above summaries, including the date and time of assessment and reasons if known as to why a scheduled assessment was not conducted. Listings will also include what abnormality is satisfied at each visit pre/post infusion.

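### SAP 6.6.2 takes the latest same-day post-infusion vital signs, so a reading recorded after the protocol's 1-hour measurement replaces it in the by-visit summaries

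*SAP*

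**What the plan says.** Protocol 8.4.1 (Vital Signs) says that body temperature, heart rate, respiratory rate and blood pressure "will be assessed before and 1 hour after the completion of each infusion". The Schedule of Activities and SAP 16.4.1 repeat this timing. For blood pressure and heart rate, three readings are taken and only the third is recorded.

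SAP 6.5 states: "Measurements taken at unscheduled visits (including retests) can be considered for the by-visit summaries", subject to the windowing rules. SAP 6.6.2 then says how to choose when a window holds several results:

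- Scope: "the following rules will be applied to select the appropriate value to be used for post-baseline by visit summaries".
- Eligible readings: "Only the vital signs assessed prior or after an infusion of the study drug, on the day of the infusion, are considered".
- Before and after: "note that pre-infusion and post-infusion assessments should be considered separately".
- Same date: "If more than one assessment is on the same date, take the latest based on time".

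No part of SAP 6.6.2 refers to the 1-hour timepoint. The selected values feed two outputs in SAP 16.4.5: the values at each visit and "Change from pre-dose to post-dose at each visit" (all parameters except weight). SAP 16.4.5 also plans the incidence of markedly abnormal values by age group and parameter, together with listings that flag abnormalities before and after infusion.

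**The concern.** For the pre-infusion value, taking the latest reading is sensible because it is the one nearest the start of the infusion. After the infusion, the same rule moves away from the protocol's timepoint whenever someone records a further reading.

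Those further readings are unlikely to arise at random. Protocol 4.1 and 6.1 do not require participants to stay once the infusion ends, unless the investigator sees a medical need. Readings later than 1 hour should therefore come mostly from participants who were held back, often because of a reaction. Which timepoint enters the summary then depends on how the participant responded.

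Protocol 9.3.5 names vital signs as a safety endpoint, and the trial's question is whether shorter infusions are tolerated. A pre-to-post change taken at 1 hour for most participants and at some later time for those who reacted is not a like-for-like comparison across infusions.

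**Working it through.** The plan states no figure that depends on this rule, so there is nothing to reproduce. The check applies the rule to assumed readings.

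**When the rule acts.** The triplicate blood pressure and heart rate readings do not trigger it, because only the third is recorded. Neither document schedules another post-infusion set. The rule therefore matters only when an extra same-day post-infusion reading is recorded, which SAP 6.5 makes eligible.

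**What it selects.** The table uses assumed systolic pressures in mmHg, with baseline and pre-infusion both 125. Change = selected post-infusion value - 125.

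| Assumed sequence | Latest (SAP 6.6.2) | Closest to 1 hour |
|---|---|---|
| A: 122 at 1 h only | 122, change -3 | 122, change -3 |
| B: 84 at 20 min, 112 at 1 h | 112, change -13 | 112, change -13 |
| C: 84 at 20 min, 88 at 1 h, 118 at 2 h | 118, change -7 | 88, change -37 |
| D: 118 at 1 h, 86 at 3 h | 86, change -39 | 118, change -7 |
| E: 82 during infusion, 120 at 1 h | 120, change -5 | 120, change -5 |

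The two rules differ only in C and D, where a reading later than 1 hour exists. In C the recovered value displaces the abnormal 1-hour value. In D a worse late value displaces a normal one. In B both rules omit the early low reading. In E the low reading is left out by the eligibility sentence, which names only readings before or after an infusion, and not by the latest-reading rule.

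**Size for one participant.** Assume 120 before, 85 at 1 hour and 118 at 2 hours.

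- Protocol timepoint: 85 - 120 = -35 mmHg.
- SAP rule: 118 - 120 = -2 mmHg.
- Difference: 118 - 85 = 33 mmHg.
- Shift in the visit mean: 33/n. At the maximum enrolment, n = 14, this is 33/14 = 2.4 mmHg. At an assumed n = 5 it is 33/5 = 6.6 mmHg. Smaller n is realistic at later visits, because participants stop infusions once they reach the shortest planned duration or have a second reaction.

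**How many infusions could be affected by a reaction.** A second reaction ends treatment, so at most 14 x 2 = 28 infusions can have one, out of at most 14 x 9 = 126. This is a ceiling: a reaction need not change vital signs, and a later reading need not be recorded.

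**PCSA incidence.** SAP 6.6.2 limits its selection rule to by-visit summaries. SAP 16.4.5 reports PCSA over the study treatment period and does not say whether it uses the selected values or every recorded reading. The adult low systolic criterion in SAP 16.4.4 needs a value of 90 or less and a fall from baseline of at least 20. If baseline is also taken as 120, the 1-hour value of 85 meets it (change -35) and 118 does not. If PCSA uses all readings, the participant is counted; if it uses selected values, the participant is missed. In addition, SAP 16.4.3 defines change from baseline only for pre-dose values, so the post-infusion calculation is left open.

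**The case against.** The strongest case against has four parts.

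**The condition may be rare.** Displacement needs a same-day reading after the 1-hour one, and neither document asks for it. That extra readings continue until recovery is an assumption about site practice, and the public documents do not show whether the eCRF pages hold repeats. This stands, and it limits how often the rule matters. It does not justify the rule, since nothing in the SAP explains why a later reading should be preferred to the protocol's timepoint.

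**The direction is not fixed.** Sequence D shows the latest-reading rule picking up a delayed abnormality that a 1-hour rule would leave out of the by-visit summary. This also stands. It is the reason to pair a fixed timepoint for by-visit summaries with an abnormality count over all readings.

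**Reactions are captured elsewhere.** Hypotension, hypertension, tachycardia, tachypnea and fever are listed reaction terms in Protocol 8.5.6. Infusion associated reactions are adverse events of special interest, reported within 24 hours and tabulated under SAP 16.1.8. The primary and secondary endpoints rest on reactions and infusion duration, not on these summaries. This stands in full. A reader might infer that the rule hides reactions; the documents do not support that.

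**The abnormality count may not be touched.** A reader might infer that PCSA incidence loses the event, a shift of 1/14 = 7.1 percentage points. That would follow only if PCSA used the selected values, which the SAP does not say.

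**Conclusion.** The point holds in a limited form. SAP 6.6.2 departs from the protocol's 1-hour measurement whenever a later same-day reading is recorded, and this is most likely in participants kept on site for medical reasons. The consequence is confined to the by-visit values and the pre-to-post change. In the assumed example it is 33 mmHg for one participant and 2.4 mmHg on a visit mean at n = 14, and more where fewer participants are infused. The blood pressures are illustrative, so the figures show what one such case does and not how often it will occur.

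Two stronger statements are not supported: that every infusion with a reaction loses its abnormal reading, and that the bias always runs toward normal. If the 1-hour reading is the last of the day, the SAP selects exactly the protocol's measurement. Whether PCSA incidence is affected is unspecified, which is a gap to close and not a demonstrated loss.

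**What to change.** In SAP 6.6.2, keep the latest reading for the pre-infusion value. For the post-infusion value, use the reading closest to 1 hour after completion of the infusion.

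In SAP 16.4.5, state that PCSA incidence uses all recorded on-treatment readings, including unscheduled ones, so that an abnormal value at any time counts. The same sentence should say how change from baseline is computed for post-infusion readings. This recovers the low values in sequences B, C and D, and the one in E if in-infusion readings are recorded.

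The cost is a few sentences in the SAP and a small programming change. No new data are needed. PCSA incidence may become slightly less favourable, and a delayed abnormality such as that in D would appear in the PCSA count but not in the by-visit mean.

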6.7 STATISTICAL TESTS

No formal statistical test will be performed in this study.

6.8 COMMON CALCULATIONS

For the below "Visit X" corresponds to post-baseline visits for all X. For quantitative measurements, change and percent change from baseline will be calculated as:

- Change from baseline at visit X = Test Value at Visit X Baseline Value
- Percentage change from baseline = 100*(Test Value at Visit X Baseline Value)/
 Baseline Value

Conversion from weight (lb) to weight (kg) is given by:

• Weight (kg) = 0.453592*Weight(lb)

6.9 SOFTWARE VERSION

All analyses will be conducted using SAS version 9.4 or above.

7 STATISTICAL CONSIDERATIONS

In general unless otherwise specified, descriptive statistics will be provided on observed cases only eg, for by-visit summaries only participants with non-missing values at that visit will be included in the analysis at that visit. Data will be summarized by cohorts 1-4 pooled. There will be no comparisons between any of the cohorts for all analysis.

The following descriptive statistics will be used as applicable to summarize the study data unless stated otherwise:

Document: \\ieedo

Author:

vnasc01\BIOSdata\Sanofi\Fabrazyme\IAB16602\Biostatistics\Documentation\SAP\SAP\Sanofi\Final

Version Number:

Version\lps17726-16-1-9-sap.docx

Version Date:

Template No.: CS_TP_BS016 Revision 7 Reference: CS_WI_BS005

Effective Date: 01Nov2021

PROTOCOL LPS17726

Analysis Plan Template

Page 31 of 65

- Continuous data will be summarized using the number of observations available (number, arithmetic mean, standard deviation [SD], minimum, median, 1st quartile, 3rd quartile, and maximum).
- Categorical data will be summarized using count and percentage (the percentage of participants in each category relative to the total number of participants in the relevant analysis set or relative to the total number of participants in the relevant analysis set, with assessments available [where appropriate]) in each category.

7.1 MULTICENTER STUDIES

This study will be conducted by multiple investigators at multiple centers. Data from all centers will be pooled for statistical analyses.

7.2 Intercurrent Events (ICE)

The intercurrent events in this study are defined as follows:

- ICE1 = Premature discontinuation of study treatment.
- ICE2 = Pre-medications are not given as described within the protocol.

The handling of the intercurrent events will be as follows:

For primary and secondary endpoints:

Management of ICE1 = A while-on-treatment approach will be applied in case of premature discontinuation of the study treatment, where the value of the endpoint will be derived from the infusions actually received.

Management of ICE2 = A treatment policy approach will be applied in the case pre-medications are not given as described within the protocol, meaning the value for the endpoint of interest will be used regardless of whether different pre-medications are given to those listed within the

Document: \\ieedc

Author:

vnasc01\BIOSdata\Sanofi\Fabrazyme\IAB16602\Biostatistics\Documentation\SAP\SAP\Sanofi\Final

Version\lps17726-16-1-9-sap.docx

Version Number: Final V1.0

Version Date: 22Oct2024

Template No.: CS_TP_BS016 Revision 7 Reference: CS_WI_BS005

Effective Date: 01Nov2021

PROTOCOL LPS17726

Analysis Plan Template

Page 32 of 65

protocol, administration of the pre-medications are different to what is provided on the protocol or in an absence of pre-medication being administered.

For exploratory endpoints:

Management of ICE1 = A treatment policy approach will be applied in the case of premature discontinuation of the study treatment, meaning the value for the endpoint of interest will be used regardless of whether study treatment was discontinued prematurely or not.

Management of ICE2 = A treatment policy approach will be applied in the case pre-medications are not given as described within the protocol, meaning the value for the endpoint of interest will be used regardless of whether different pre-medications are given to those listed within the protocol, administration of the pre-medications are different to what is provided on the protocol or in an absence of pre-medication being administered.

7.3 MISSING DATA

7.3.1 PRIMARY, SECONDARY AND EXPLORATORY ENDPOINTS

7.3.1.1 PRIMARY ENDPOINTS

7.3.1.1.1 ACTUAL INFUSION DURATION

If actual infusion duration, see Section 15.1.2, cannot be calculated due to a partial date and/or time combination of any terms in the derivation, including interruption times then the actual duration will be set to the planned duration. Missing or partial dates for infusion start/stop and interruption times will not be imputed.

7.3.1.1.2 ACTUAL SHORTEST TOLERATED INFUSION DURATION

Participants never observed to tolerate any infusion during the study treatment period will have

Document: \\ieedc-

vnasc01\BIOSdata\Sanofi\Fabrazyme\IAB16602\Biostatistics\Documentation\SAP\SAP\Sanofi\Final

Version\lps17726-16-1-9-sap.docx

Author: Version Number: Final V1.0

Version Date: 22Oct2024

Template No.: CS_TP_BS016 Revision 7 Reference: CS_WI_BS005

Effective Date: 01Nov2021

PROTOCOL LPS17726

Analysis Plan Template

Page 33 of 65

their actual shortest tolerated duration set to their mean (average) pre-study infusion duration. If all pre-study durations are missing and the participant does not tolerate any infusion during the study treatment period, then shortest tolerated infusion duration will be considered missing.

